**Table 2\_adj: Primary outcome of 11 mg QD vs. 5 mg BID Initiators**

	11 mg QD Initiators N=	5 mg BID Initiators N=	p-value**
Primary Outcome	OR (95% CI)*	Ref	
MCID Improvement in difference in CDAI from initiation to 6 month visit			

\*The adjusted OR (95% CI) will give the odds of having MCID improvement in the 11 mg QD initiator group as compared to the odds in the 5 mg BID initiator group after adjusting for covariates; the 5 mg BID initiator group will be the reference group.

\*\*The p-value will be reported from a logistic regression model considering the 11 mg QD vs. 5 mg BID group adjusting for covariates that differ between the 11 mg QD and 5 mg BID initiators according to the primary outcome.

**Table 3\_adj: Secondary outcomes of 11 mg QD vs. 5 mg BID\***

	11 mg QD Initiators N=	5 mg BID Initiators N=	p-value†
Continuous outcomes	Least squares mean (95% CI)*	Least squares mean (95% CI)*	
Change from baseline CDAI to 6 month CDAI			
Change from baseline mHAQ to 6 month mHAQ			
Change from baseline HAQ to 6 month HAQ			
Change from baseline mDAS to 6 month mDAS			
Change from baseline DAS ESR to 6 month DAS ESR			
Change from baseline DAS CRP to 6 month DAS CRP			

	11 mg QD Initiators N=	5 mg BID Initiators N=	p-value †
Change from baseline pain VAS (0-100) to 6 month pain VAS			
Change from baseline fatigue (0 to 100) to 6 month fatigue			
Change from baseline EQ-5D (0-1) to 6 month EQ-5D			
Binary outcomes measured at 6 months	OR (95% CI)**	1 Ref	
Achievement of LDA ‡			
Achievement of LDA §			
Achievement of Remission 			
Achievement of Remission ¶			
Improvement in mHAQ $\geq$ 0.25**			
Improvement in HAQ $\geq$ 0.22**			
mACR20 ††			
mACR50 ††			
mACR70 ††			

\*For continuous outcomes, the least squares means (95% CI) will be reported from a linear regression model adjusted for covariates considering the 11 mg QD and 5 mg BID initiator groups. For binary outcomes, the adjusted OR (95% CI) will give the odds of achievement of the outcome in the 11 mg QD initiator group as compared to the odds in the 5 mg BID initiator group after adjusting for covariates; the 5 mg BID initiator group will be the reference group.

†For continuous outcomes, the p-value will be reported from a linear regression model for the outcome adjusted for covariates considering the mean difference between the 11 mg QD and 5 mg BID initiators. For binary outcomes, the p-value will be calculated from a logistic regression model considering the 11 mg QD vs. 5 mg BID groups adjusting for covariates.

‡Low Disease Activity defined as 6-month CDAI $\leq$ 10 among those with baseline CDAI $>$ 10

§Low Disease Activity defined as 6-month CDAI $\leq$ 10 for all patients

||Remission defined as 6-month CDAI $\leq$ 2.8 among those with baseline CDAI $>$ 2.8

¶Remission defined as 6-month CDAI $\leq$ 2.8 for all patients

\*\*Improvement in mHAQ will be calculated only for patients with baseline mHAQ $\geq$ 0.25 and improvement in HAQ will be calculated only for patients with baseline HAQ $\geq$ 0.22

††modified ACR: based on 2 out of 4 measures (not using ESR or CRP)

Table 2\_adj will present the primary outcome and Table 3\_adj will present the secondary outcomes for the second look incorporating the adjusted analysis.

**Table 3\_switchers. Number of initiators of 11 mg QD (from the cohort of 11 mg QD initiations considered in Tables 1-3) that switch\* to 5 mg BID by their 6 month follow-up visit.**

\*Switch defined as discontinued 11 mg QD and initiated or restarted 5 mg BID.

**Table 4. Patient Demographic and Clinical Characteristics for the cohort of patients that switched from Tofacitinib 5 mg BID to Tofacitinib 11 mg QD**

At time of Tofacitinib 5 mg initiation	Patients that switched from Tofacitinib 5 mg BID to Tofacitinib 11 mg QD N=
Patient Characteristics	
Female: n (%)	
Age: Mean ± SD	
Duration of RA: Mean ± SD	
Race: n (%)	
White	
Black	
Asian	
Other	
Missing	
Race: N (%)	
White	
Non-white	
Weight: Mean ± SD	
BMI	
Normal/underweight: n (%)	
Overweight: n (%)	
Obese: n (%)	
Missing	
Comorbid conditions: n (%)	
Hx of Hypertension	
Hx of Diabetes	
Hx of Malignancy*	
Hx of CV disease**	
Current use of statins	
RA Treatment History	
Prior number of cDMARDs: Median (IQR)	
Prior cDMARD Use: N (%)	
0	
1	
2	
3 +	
Prior TNF Use	
0	
1	
2+	

**Table 4 continued**

At time of Tofacitinib 5 mg initiation	Patients that switched from Tofacitinib 5 mg BID to Tofacitinib 11 mg QD N=
Prior non-TNF Use	
0	
1	
2+	
Prior Biologic Use	
0	
1	
2	
3+	
Current concomitant therapy	
Monotherapy	
Combo w/MTX alone	
Combo w/other cDMARD (not MTX)	
Combo w/MTX + other cDMARD	
Current medication at the time of initiation	
Prednisone use: n (%)	
Prednisone dose among users	
≤10 mg	
>10 mg	
Disease Activity: Mean ± SD	
Tender Joint Count (28)	
Swollen Joint Count (28)	
Physician Global Assessment (0-100)	
Patient Global Assessment (0-100)	
CDAI (0-76): Mean ± SD	
Disease Activity Category: N (%)	
Remission (CDAI ≤ 2.8)	
Low (2.8 < CDAI ≤ 10)	
Moderate (10 < CDAI ≤ 22)	
Severe (22 < CDAI)	
Patient Pain (0-100)	
Patient reported fatigue (0-100)	
EQ-5D (0-1)	
mDAS: Mean ± SD	
DAS ESR: Mean ± SD	
DAS CRP: Mean ± SD	

**Table 4 continued**

At time of Tofacitinib 5 mg initiation	Patients that switched from Tofacitinib 5 mg BID to Tofacitinib 11 mg QD N=
Line of Therapy d : N (%)	
1 st	
2 nd	
3 rd	
4 th	

SD = Standard Deviation

IQR = Interquartile Range: 25th percentile, 75th percentile

**Table 5. Outcomes at 6 months from switch of the cohort of patients that switched from Tofacitinib 5 mg BID to Tofacitinib 11 mg QD**

		Switchers
	Total Patients	N
Continuous Outcomes: Change from Switch to 6 Months a		
		Mean ± SD
	CDAI (N miss =)	
	mHAQ (N miss =)	
	HAQ (N miss =)	
	mDAS (N miss =)	
	DAS ESR (N miss =)	
	DAS CRP (N miss =)	
	Patient Pain (N miss =)	
	Patient Fatigue b (N miss =)	
	EQ-5D (N miss =)	
Binary Outcomes: Measured at 6 Months		
		N (%)
	Worsening CDAI c	
	Achievement of Low Disease Activity d	
	Achievement of Low Disease Activity e	
	Achievement of Remission f	
	Achievement of Remission g	
	Improvement in mHAQ ≥ 0.25 h	
	Improvement in HAQ ≥ 0.22 h	
	mACR20 i	
	mACR50 i	
	mACR70 i	

Nmiss = number of observations with missing values for the specified variable; SD = Standard deviation

a Change defined as value at 6-month post-switch visit minus value at switch

b Patient fatigue scale defined from 0='Fatigue is no problem' to 100='Fatigue is a major problem'

c Worsening defined for patients in remission, low, or moderate disease activity at switch and worsening by at least one category at 6-months post-switch

d Low Disease Activity defined as 6-month post-switch CDAI ≤ 10 among those with CDAI > 10 at switch

e Low Disease Activity defined as 6-month post-switch CDAI ≤ 10 for all patients

f Remission defined as 6-month post-switch CDAI ≤ 2.8 among those with CDAI > 2.8 at switch

g Remission defined as 6-month post-switch CDAI ≤ 2.8 for all patients

h Improvement in mHAQ calculated only for patients with mHAQ at switch ≥ 0.25, and improvement in HAQ calculated only for patients with HAQ at switch ≥ 0.22

i modified ACR: based on 2 out of 4 measures (not using ESR or CRP)

**Table 5\_switchers. Number of switchers from 5 mg BID to 11 mg QD (from the cohort considered in Tables 4 and 5) that switch\* to 5 mg BID by their 6 month follow-up visit.**

\*Switch defined as discontinued 11 mg QD and initiated or restarted 5 mg BID.

## Appendix:

### Pfizer QD Power Calculations:

Since the approval of Tofacitinib 11 mg QD in 2/2016, we have been assessing whether there are enough patients to adequately compare these patients to patients on 5 mg BID. Power calculations below indicate that to detect a reasonable difference of 15% in the percentage meeting MCID in CDAI, about 300-500 patients per group would be needed.

With the following assumptions,

- Consider the dichotomous outcome of meeting MCID in CDAI
- We would like to have 90% power to detect a difference between the two groups in percentage meeting MCID in CDAI
- We would like to have a low chance (alpha of 5%) of declaring that there is a difference in the outcomes between the two groups when in actuality there is not (type I error)

The following table gives the number needed per group and total number needed for different scenarios of meeting MCID for CDAI and percent of patients who are available under common support (e.g. percent of patients in the control group that are similar enough to the treatment group so that we are comfortable that the two cohorts are similar). If we assume that the percentage meeting MCID in CDAI is 50%, the following sample sizes are required.

Difference between the two groups in percentage meeting MCID in CDAI that can be detected	Analyzable Data Set, N per group	% under common support	N per group required to recruit	Total N required to recruit
10%	535	50%	1070	2140
10%	535	75%	713	1426
15%	237	50%	474	948
15%	237	75%	316	632
20%	131	50%	262	524
20%	131	75%	175	350
25%	84	50%	168	336
25%	84	75%	112	224

### **Preliminary Projections:**

The next step was to consider when an adequate number of patients would be reached. For this, we completed preliminary projections.

Under different scenarios for projections of the total number of Tofacitinib 11 mg QD initiators over time, we find that there will be:

- About 125-135 Tofacitinib 11 mg QD initiators with 6 month follow-up visits by the end of March 2018 (e.g. report ready for Day 80 due 6/18/2018)
- About 150-170 Tofacitinib 11 mg QD initiators with 6 month follow-up visits by the end of June 2018 (e.g. report ready for Day 120 due 9/14/2018)
- About 180-220 Tofacitinib 11 mg QD initiators with 6 month follow-up visits by the end of 2018
- About 260-320 Tofacitinib 11 mg QD initiators with 6 month follow-up visits by the end of 2019

Note that there is the need for patients that have a follow-up visit at 6 months (+/- 3 months) in order to assess efficacy at 6 months. As of February 2017, about 60% of the total number of initiators had at least one follow-up visit.

### **Interim Look:**

Oftentimes when designing a study, investigators would like to get an initial look at the data in order to inform future decisions. While it is not possible to continually re-analyze the data, it is possible to do pre-planned interim looks at the data prior to when there are sufficient patients as per the power calculation. There are however drawbacks to looking at the data prematurely. There is the possibility that incorrect inferences are drawn due to the limited information. This is particularly an issue if the patients accrued at the beginning of the study are somehow different from later patients. Also, when computing the final outcome of the study, it is necessary to adjust for the fact that you have already taken a look at the data. This means that if you are considering that a p-value less than 0.05 would indicate a difference between the two groups, then if you have already taken a look, the p-value required to say that there is a difference between the two groups would need to be less than 0.05.

We are now proposing to consider two interim looks at the data – one at 33% accrual and another at 50% accrual. If we assume that we wish to detect a change in 15% from the proposed MCID of CDAI of 50% with 75% under common support, we would need 237/group analyzable and the p-value for the first interim look would need to be less than 0.001 to be considered statistically significant, a p-value for the second interim look would need to be less than 0.003 to be considered statistically significant and a p-value for the final look would need to be less than 0.049 to be considered statistically significant.

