### Population for Overall Aim:

For the primary analysis comparing QD to BID patients, we will consider those patients who initiated tofa 5 mg BID on or after February 2016 and those that initiated tofa 11 mg QD after it became available in February 2016. Although the sample size will be smaller than if we consider all tofa 5 mg BID patients, the addition of those patients may introduce noise since there is the possibility that they could differ from the more recent initiators. Therefore, we will consider the cleaner cohort of all patients initiating tofa on or after February 2016.

In order to adequately measure the outcome, the initiators will also be required to have a follow-up visit at 6 months (+/- 3 months) after tofacitinib initiation.

The data cut to be used will be the most recent available.

With regards to dosing, patients can be categorized as follows:

QD dosing: once-daily tofacitinib 11mg

BID dosing: 5mg twice-daily

Other: other dosages including 10 mg and will also include not specified

Those in the "other" category will not be considered in these analyses.

The first initial look at the data has indicated that the tofa 5 mg BID group differs on some characteristics from the tofa 11 mg QD group. To account for these differences, in a second look at the data, we propose to consider models adjusted for no more than 10 covariates. This will provide a robust analysis, while preserving sample size. The full propensity score analysis will be done in the final look at the data when the sample size is large enough (as per preliminary power calculations on page 23).

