**Table 1 continued**

At time of Tofacitinib initiation	11 mg QD N=	5 mg BID N=	Standardized difference
Line of therapy			
1 st			
2 nd			
3 rd			
4 th			

SD = Standard Deviation

IQR = Interquartile Range: 25th percentile, 75th percentile

Standardized differences rather than p-values can be more informative regarding the actual size of the difference between the two groups; hence, it is suggested that they be used rather than p-values to inform which variables are to be included in the propensity score model.

\*The scale ranges from 0-100 with 0 being fatigue is no problem to 100 fatigue is a major problem.

**Table 1a. Patient Demographic and Clinical Characteristics for Tofacitinib Initiators by Dose (5 mg BID and 11 mg QD) after Propensity Score Matching.**

Repeat Table 1 in the Propensity Score Matched cohort. *Table only generated for the final analysis.*

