## Statistical Analysis Plan (SAP) - Pfizer 054c

### Title: QD Efficacy Analysis – Addendum

As a complement to the primary analysis, an exploratory analysis will be conducted using the full pre- matched analysis population (N = 450). In addition to the results, we will provide a summary describing new analyses, methods used including differences from prior methods, and interpretation of results.

**Objective 1:** Repeat the primary analyses (Tables 1 – 3\_adj) using the full analysis population (N = 450).

New analyses will be incorporated into the existing report and tables will be named so as to avoid confusion with pre-existing analyses. Along with each newly analyzed section, we will describe any changes from the previous analyses and we will provide interpretation of all results.

Analysis: We will update the analyses in the following ways:

Table 1: Will not be altered. This table shows baseline characteristics of the full analysis population.

Table 1a: Will not be re-generated. Table 1a showed baseline characteristics among the PS matched population and will be excluded from this analysis.

Table 2: Will be generated using the full analysis population.

Table 2\_adj: Will be generated using the full analysis population. The unadjusted estimate will remain unadjusted, and the adjusted estimate will be generated using a model which considers imbalanced covariates (as defined by the standardized differences from Table 1). We will perform model selection to ensure that we optimize the combination of a high level of explanatory power and a concise number of degrees of freedom.

Table 2a: Will be generated using the full analysis population. Table 2b: Will be generated using the full analysis population. Table 3: Will be generated using the full analysis population.

Table 3\_adj: Will be generated using the full analysis population. Adjusted estimates will be calculated similar to those in Table 2\_adj.

**Objective 2:** Provide detailed information on exclusion criteria used when selecting the 297 eligible QD initiators (out of the original 611 initiators) as well as the 153 BID initiators (out of the original 258 initiators).

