Analysis: We will update the sample selection figure to reflect the sample derived from the end of September 2018 version of the registry. Reasons for exclusion will be detailed and will include: initiated treatment too late (i.e. after 3/31/2018) and so had not reached time for 6 month visit, no 6 month visit despite having initiated treatment

longer than 6 months ago, no valid CDAI at initiation, and no valid CDAI at 6 months despite attending visit.

	5 mg BID (N/%)	11 mg QD (N/%)
Initiated after 3/31/2018 (not reached 6 months)		
No 6 month visit		
No valid CDAI at initiation		
No valid CDAI at attended 6 month visit		

In addition to the analyses, we will provide an interpretation of the results, including thoughts on the reasons for the listed difference. We will also assess the potential biases that may be introduced into the analyses due to the exclusion criteria.

**Objective 3:** Repeat the primary analyses (Tables 1 – 3\_adj) using a propensity score trimmed population.

To ensure the adjusted analyses do not extrapolate due to the use of dissimilar patients, the propensity score which was previously used to match patients can be used to trim the population of the initiations for which there is no similar initiation in the other group – carrying out the multivariable adjustment for patients on “common support” across the covariates of interest. The propensity score distribution will be examined in both populations and each population will be trimmed for extreme values: patients in one group with propensity scores higher or lower than scores in the other group will be “trimmed” (i.e., excluded from analyses). Only patients with scores overlapping both distributions will be included in the analysis.

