**Proposed Analyses:**

1. Repeat all analyses (Tables 1 – NI) using more recent data

Of the previously defined cohort of 869 tofacitinib initiators (611 initiators of 11 mg QD, and 258 initiators of 5 mg BID) who initiated on or after 2016/02/01, 306 patients (245 initiators of 11 mg QD, and 61 initiators of 5 mg BID) had no available follow-up visits post-initiation using the original 2018/09/30 version of the RA registry, and so were excluded from analysis. In order to remedy the high proportion of initiators with no follow-up, we will consult the most recent data available (RA registry version 2019/08/31) in order to provide the most complete understanding of the availability of follow-up for these patients.

Preliminary investigations indicate that 117 of these 306 initiators have an eligible six-month follow-up visit available and can be included in further analyses (Appendix Table). With the addition of these patients, we would proceed to further analyses with 401 (66%) out of the 611 initiators of 11 mg QD, and 172 (67%) out of the 258 initiators of 5 mg BID (Table 2). After updating the eligible sample and replicating all analyses, the report previously delivered on CCI [REDACTED] will be re-created. (Note: final analyses will also require valid CDAL measurements at initiation and six-month follow-up, which will exclude a small number of patients from these cohorts)

Table 2. Tofacitinib initiators' eligibility status categories by initiation dose, using 2019/08/31 version of RA database

	All Initiators	11 mg QD	5 mg BID
After 1/31/2016	869	611	258
No follow-up	113 (13%)	79 (13%)	34 (13%)
First follow-up not during first year	67 (8%)	51 (8%)	16 (6%)
Follow-up within first year BUT no six-month visit	116 (13%)	80 (13%)	36 (14%)
Eligible six-month visit	573 (66%)	401 (66%)	172 (67%)

2. Perform sensitivity analysis of primary outcome

Using the updated eligible cohort detailed in Table 2 above, 34% of initiators will remain ineligible for analysis. We will present an additional table similar to Addendum Full Table 2 CCI which will include all 869 initiators of 11 mg QD and 5 mg BID, treating those who are not eligible due to lack of six-month follow-up visit as not achieving MCID in CDAI.

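### The propensity-matched final look is planned at 237 analysable patients per group, but the BID arm offers at most 153 (September 2018) or 172 (August 2019) before matching, so its 90% power should be restated

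*SAP*

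**What the plan says.** **The planned look.** SAP, Population for Overall Aim: "The full propensity score analysis will be done in the final look at the data when the sample size is large enough", with a pointer to the preliminary power calculations. Those calculations (SAP Appendix; protocol section 9.5) assume a 50% response rate, 90% power and 5% alpha, call 15 points a reasonable difference, and give 237 per group for it. SAP, Interim Look, repeats that for 15 points and 75% common support "we would need 237/group analyzable". It sets interim looks at 33% and 50% accrual (p below 0.001 and 0.003), and for the last look "a p-value for the final look would need to be less than 0.049 to be considered statistically significant".

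**September 2018.** The Table 1a shell, which describes the matched cohort, carries the note "Table only generated for the final analysis". The addendum, Objective 1, reports in the past tense that "Table 1a showed baseline characteristics among the PS matched population" and puts the population before matching at 450. Objective 2 splits this into 297 QD initiators "as well as the 153 BID initiators" and refers to "the sample derived from the end of September 2018 version of the registry".

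**August 2019.** The later addendum, Proposed Analyses item 1, repeats all analyses on the August 2019 registry for the same 869 initiators: "After updating the eligible sample and replicating all analyses, the report previously delivered on" a redacted date is to be re-created. Its Table 2 counts 401 QD and 172 BID initiators with an eligible six-month visit. A requirement for valid CDAI at both visits will remove a few more. The Justification section then widens the visit window to the whole first year, giving 689 patients.

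**The concern.** The matched tables belong to the final analysis, and the final analysis was to wait for a sample that the power calculations would call large enough. The matched tables were nevertheless produced from a BID pool well below 237, and are to be repeated from a pool that is still below it. No visible text says that the planned size was missed, restates the power, or says which cut carries the 0.049 threshold.

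The stake is interpretation. The hypothesis in both documents is that the two regimens perform similarly, so a non-significant difference is the result most likely to be taken as support. A reader relying on the Appendix would assume 90% power for 15 points behind that result. The protocol (section 12) also foresees reporting results to a regulator.

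**Working it through.** **Inputs.** Response 50% vs 65%, 90% power, alpha 5% (sidedness not stated), 237 per group, 75% common support: SAP Appendix. Threshold 0.049: Interim Look. Pools 297/153: addendum, Objective 2. Pools 401/172: later addendum, Table 2.

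**1. The plan's own figure.** With mean rate 0.575,

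n = [1.960·√(2·0.575·0.425) + 1.282·√(0.5·0.5 + 0.65·0.35)]² / 0.15² = 226.2, so 227 per group, or 240 with continuity correction.

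The stated 237 lies between them, within 3% of the corrected value. One-sided versions give 185 to 203 and do not fit, so the test is taken as two-sided. The recruitment figure is 237/0.75 = 316, as stated.

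**2. Counts against 237.** 153/237 = 65% and 172/237 = 73%. Only BID is short; the QD pools (297 and 401) exceed 237 before matching. The cohort is closed at 258 BID initiators: reaching 237 would need 237/258 = 92% eligible, against 172/258 = 67% found. The widened window adds Table 2's patients who had first-year follow-up but no six-month visit: 172 + 36 = 208 BID and 401 + 80 = 481 QD (total 689). That is 81% of 258, and 208 is still below 237.

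**3. Power at two-sided 0.049 (z = 1.969).** For equal arms,

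power = Φ{[0.15 − 1.969·√(2·0.575·0.425/n)] / √(0.4775/n)}.

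At n = 172: (0.15 − 1.969·0.0533)/0.0527 = 0.855, so 80%. For unequal arms the same approximation is used with each arm's own size. The equivalent number per group is 2·n₁·n₂/(n₁+n₂), and its ratio to 237 is the share of planned information.

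| Analysed BID vs QD | Equivalent per group | Share of plan | Power |
|---|---|---|---|
| Plan, 237 vs 237 | 237 | 100% | 91% |
| 2018, one-to-one, no loss, 153 vs 153 | 153 | 65% | 76% |
| 2018, everyone, 153 vs 297 | 202 | 85% | 86% |
| 2019, one-to-one, no loss, 172 vs 172 | 172 | 73% | 80% |
| 2019, 2:1, no loss, 172 vs 344 | 229 | 97% | 90% |
| 2019, everyone, 172 vs 401 | 241 | 102% | 92% |
| 2018, 75% support, one-to-one, 115 vs 115 | 115 | 49% | 63% |
| 2019, 75% support, one-to-one, 129 vs 129 | 129 | 54% | 68% |
| 2019, 75% support, all retained, 129 vs 301 | 181 | 76% | 82–83% |
| Widened window, one-to-one, no loss, 208 vs 208 | 208 | 88% | 87% |

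The 75% is applied to both arms, as the SAP's recruitment column does (0.75·172 = 129; 0.75·401 = 301). The range in the second-last row but for the widened window reflects which arm has the higher response rate.

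**4. Difference detectable with 90% power, one-to-one.** 14.7 points at 237, 17.2 at 172, about 18 at 153, 19.7 at 129.

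**5. Type I error.** Nominal levels 0.001, 0.003 and 0.049 at information 0.33, 0.50 and 1.00 give about 5.0% overall. If August 2019 replaces September 2018 as the final look, the result is 4.96% to 5.07%, depending on the information fraction assumed.

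**The case against.** The strongest reply is that lower power is assumed, not shown. No visible text gives a matching ratio. For August 2019, a lossless 2:1 match has about 90% power, and all 401 vs 172 carry 102% of the planned information. This stands, and it is why the power loss must be stated conditionally. It does not remove the point: the per-group count is missed at any ratio, the 0.01 caliper and the CDAI requirement take further patients, and at the SAP's own 75% support no ratio brings 2019 above about 83%. For September 2018 even the full pool reaches only 86%.

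Second, 237 is a planning figure. The power table has other rows (535, 131, 84), and the Interim Look paragraph is worded conditionally. A reader might infer that the SAP forbids matching below 237; it does not say so. What it does is describe the matched look as having that size and power.

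Third, a reader might infer that two matched runs inflate the false-positive rate. It would be about 6.2% to 6.9% only if either cut could be declared positive at 0.049, and no visible text permits that. The SAP's rule of using the most recent data cut, and the plan to re-create the delivered report, favour August 2019 replacing September 2018.

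Fourth, other samples exist. The 869-patient sensitivity analysis includes all 258 BID initiators, and the addendum adds full-population and trimmed analyses. These are useful, but they are not the matched look that the power statement describes.

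Finally, parts of the addenda are blacked out or removed. The reference list cites a guideline on non-inferiority margins, and the later addendum's table range ends in NI, so a non-inferiority analysis probably sits in the hidden text. If it carries the similarity conclusion, the difference test matters less.

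**Conclusion.** The point holds in limited form. The matched final look is described at 237 per group with 90% power, and the visible BID pools are at most 153 and 172 before matching, so that size is not reached in either cut. The widened window, at most 208 BID, does not reach it either.

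Under one-to-one matching, power for 15 points is at most about 76% (2018) or 80% (2019). These are upper bounds, because matching losses (and, for 2019, the CDAI requirement) come on top. Planned power survives in 2019 only if the match is nearly lossless and uses most QD patients.

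The power figures rest on a two-sided test, a 50% reference rate and the normal approximation; the ratio and the matched numbers are unknown from the visible text. This is a reporting and interpretation issue of modest weight. It is not a fault in error control, and it gives no reason to alter 0.049.

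**What to change.** In the addendum:

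1. For the matched analysis, replace the statement of 237 per group and 90% power with the matched number obtained in each arm, its information as a share of plan, and the difference detectable with 90% power. Show these beside the primary result. State the matching ratio. Add that a non-significant difference is not evidence of similarity with 90% power.
2. State that the matched August 2019 analysis under the 3-to-9-month window is the inferential look at 0.049 and supersedes September 2018. Report the September 2018 matched result, and the full-population, trimmed, 689-patient and 869-patient analyses, as supportive estimates with 95% confidence intervals.

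If redacted text already sets the status of the looks, or rests the similarity conclusion on a non-inferiority analysis, a cross-reference from Population for Overall Aim and from Interim Look is enough for item 2.

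The cost is a few sentences, a table footnote, and an interval column where the Table 2 shell has only response rates and a p-value. No new data are needed.
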